8.4.3. Additional Analyses

Exploratory Analyses – PROMIS Global Health Scores

The PROMIS Global Health 10 measure comprises ten items with two summary scores for physical and mental functioning. The analyses will be performed on mITT, responder and nonresponder populations. The analyses will include:

- Both raw scores and change-from-baseline values (physical and mental domains) will be summarized as continuous variables by visit
- Number and percentage of patients with a ≥ 4.7 -point reduction from baseline (C1D1)
- Number and percentage of patients with a ≥ 4.7 -point increase from baseline (C1D1)

8.5. Safety Analysis

Safety analyses will be conducted on the safety analysis set. Safety analyses will include AEs, SAEs, vital sign measurements, clinical laboratory evaluations (hematology, chemistry) and ECGs.

8.5.1. Adverse Events

AEs will be coded using the Medical Dictionary for Regulatory Activities (MedDRA) dictionary (Version 25.0 or higher). All AEs (including SAEs) will be graded using the National Cancer Institute (NCI) Common Terminology Criteria for Adverse Events (CTCAE) version 5.0.

Summary of overall treatment emergent adverse events will be tabulated. The subject incidence of the following TEAEs will be presented: any TEAEs, any TEAEs with worst severity, treatment related TEAEs, serious TEAEs, treatment related serious TEAE, \geq grade 3 TEAEs, \geq grade 3 treatment related TEAEs, \geq grade 3 serious TEAEs, \geq grade 3 serious treatment related TEAEs, TEAEs leading to dose interruption, TEAEs leading to dose reduction, TEAEs leading to treatment discontinuation, and TEAEs leading to death.

Following TEAEs will be tabulated by System Organ Class (SOC) and Preferred Term (PT): all TEAEs, serious TEAEs, \geq grade 3 TEAEs, treatment related TEAEs, \geq grade 3 treatment related TEAEs, and serious treatment related TEAEs. Patient will be counted only once within a SOC and PT.

Following TEAEs will be tabulated by PT: all TEAEs, treatment related TEAEs, serious TEAEs, serious treatment related TEAEs, TEAEs leading to dose reduction, treatment related TEAEs leading to dose reduction, TEAEs leading to dose interruption, treatment related TEAEs leading to dose interruption, TEAEs leading to treatment discontinuation, treatment related TEAEs leading to treatment discontinuation, \geq grade 3 TEAEs, \geq grade 3 treatment related TEAEs, CMQ bacterial infection, CMQ viral infection, CMQ fungal infection, CMQ cytopenia, SMQ liver related investigations, signs and symptoms, SMQ drug related hepatic disorders – comprehensive search (narrow), \geq grade 3 CMQ bacterial infection, \geq grade 3 CMQ viral infection, \geq grade 3 CMQ fungal infection, \geq grade 3 CMQ cytopenia, \geq grade 3 SMQ liver related investigations, signs and symptoms, and \geq grade 3 SMQ drug related hepatic disorders – comprehensive search (narrow). Patient will be counted only once within a PT.

Subject listings will be provided for AEs, SAEs, AEs leading to dose interruption, AEs leading to dose reduction, AEs leading to treatment discontinuation, and deaths.

8.5.2. Laboratory Evaluations

The summary statistics of all hematology and biochemistry variables and change from baseline will be presented for each study assessment.

For shift tables, laboratory results will be classified using the CTCAE V5.0. All graded laboratory parameters will be summarized separately for hematology and biochemistry. Corresponding shift tables to compare baseline to the worst post-baseline grade within the treatment period will be provided.

For parameters of hematology and biochemistry, plots of mean / mean change from baseline with the corresponding standard error will be displayed.

Subject listing for hematology, biochemistry and urinalysis will be provided.

8.5.3. 12 Lead ECG

Descriptive statistics for ECG parameters at each time point will be presented for the values and change from baseline.

The number and percentage of patients with observed QTcF values that satisfy the following conditions will be presented by study visit. The number and percentage of patients with longest QTcF values that satisfy the following conditions will be summarized.

- ≤ 450 msec
- >450 to ≤ 480 msec
- >480 to ≤ 500 msec
- >500 msec

The number and percentage of patients having change from baseline QTcF values that satisfy the following conditions will be presented by study visit. The number and percentage of patients with longest change from baseline QTcF values that satisfy the following conditions will be summarized.

- ≤ 0 msec
- >0 to ≤ 30 msec
- >30 to ≤ 60 msec
- > 60 msec

Subject listing for ECG results will be provided.

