GLP-compliant rat and dog general toxicology/toxicokinetic studies of acute, subchronic (1 and 3 month), and chronic (6-month rat and 9-month dog) duration have been completed. The primary nonclinical toxicology finding at/near clinically relevant exposures were limited to changes in the cardiovascular (BP lowering), hepatic (transaminitis, hypertrophy/increased organ weight, and cholestasis/inflammation), renal (increased BUN, tubular changes, pigmentation, intracellular protein droplets in the epithelium), GI (decreased appetite), and hematopoietic/immunologic (anemia with regeneration and thymic/splenic lymphoid depletion) systems. Safety pharmacology studies [including human ether-à-go go related gene (hERG) (in vitro), central nervous system (rat), respiratory system (rat), and cardiovascular system (dog)] demonstrated a low likelihood of adverse and/or nonmonitorable central nervous system, respiratory, or cardiovascular system effects associated with BN101/belumosudil at clinically relevant exposure levels. Embryo-fetal toxicology (rats and rabbits) fertility (rats) studies showed that BN101/belumosudil demonstrated embryo-fetal toxicity/teratogenicity as well as reduced male fertility (reduced fertility index/sperm concentration/motility and increased abnormal sperm percentage; testes/epididymis (decreased organ weights and degenerative histopathology). Male fertility findings were generally at higher then clinically relevant exposures. In addition, there was no evidence of genotoxicity in the in vitro Bacterial Reverse Mutation Assay, the in vitro Mammalian Chromosome Aberration Test, or the in vivo

Mammalian Erythrocyte Micronucleus Test mutagenicity assay.

For more information about the BN101/belumosudil nonclinical study see the Investigator's Brochure.

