7.2 Safety Endpoints/indicators

Safety endpoints included change from baseline in vital signs, physical examination, laboratory tests (including blood routine, blood biochemistry, and urinalysis), 12-lead electrocardiogram [including Bazetts' formula-corrected QT interval (QTcB) and QTcF means and maxima], as well as AEs, including SAEs, and AEs related to study drug.

AEs (including SAEs) as well as abnormal laboratory findings will be categorized for severity according to NCI CTCAE v5.0.

Protocol Version 3.0 62 / 118 Version Date: 25 Feb 2022

Safety assessments are conducted throughout the study and, unless otherwise indicated, safety assessments begin with the signing of the ICF and continue until the end of safety follow-up after discontinuation of study drug [i.e., during the main study period, 28 ± 7 days after the final study drug administration or prior to initiation of a new treatment for systemic cGVHD, whichever occurs first].

For subjects who continue to receive study medication after the end of the subject's study, SAEs occurring during this period will continue to be collected from the subject [until 28 ± 7 days after the final study medication is administered or before starting new treatment for systemic cGVHD, whichever occurs first].

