5.2.4. Laboratory Evaluations

Hematology, chemistry, and urinalysis will be collected in CRF.

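### The SAP gives urinalysis a subject listing only, although the protocol names its change from baseline as a safety endpoint; urine changes not recorded as adverse events would go uncounted

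*SAP*

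**What the plan says.** Protocol 7.2 defines the safety endpoints as change from baseline in several measures, among them "laboratory tests (including blood routine, blood biochemistry, and urinalysis". Protocol 8.4 (Table 5) sets the urine panel, which includes protein, red cells, white cells, glucose and occult blood. Appendix 1 schedules it in the week before treatment, on Cycle 1 Day 1, on Day 1 of later cycles, at end of treatment and at the 28-day follow-up. For analysis, protocol 10.6.3 plans descriptive statistics of laboratory abnormalities and a before/after cross-tabulation of results of severity 3 or higher. It sets no panel aside.

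The SAP keeps urinalysis among the safety endpoints: section 5.2.4 states "Hematology, chemistry, and urinalysis will be collected in CRF". The analysis sections then narrow. SAP 8.5 reads "Safety analyses will include AEs, SAEs, vital sign measurements, clinical laboratory evaluations (hematology, chemistry) and ECGs". SAP 8.5.2 adds "The summary statistics of all hematology and biochemistry variables and change from baseline will be presented for each study assessment", then "All graded laboratory parameters will be summarized separately for hematology and biochemistry", with shift tables and mean plots for the same two panels. Urinalysis appears in 8.5.2 once, in its last sentence: "Subject listing for hematology, biochemistry and urinalysis will be provided".

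**The concern.** The protocol's endpoint is a change from baseline. A listing prints each patient's values but derives no change and counts no patients, so the SAP plans no output that delivers this endpoint for urine.

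The panel has some relevance for this drug. Protocol 1.3 names, among the main nonclinical findings at or near clinically relevant exposures, "renal (increased BUN, tubular changes, pigmentation, intracellular protein droplets in the epithelium". The hepatic and hematologic findings in the same sentence have dedicated groupings in SAP 8.5.1 (two liver SMQs and a cytopenia CMQ). No renal grouping is planned. Safety is part of the primary objective and of the bridging purpose. What is at stake is whether the study report can say how many patients had a new or worsened urine abnormality when the investigator did not record it as an adverse event.

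**Working it through.** No sample size, error rate or stated figure is involved, so the check sets the two documents side by side.

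**1. Planned output by panel, SAP 8.5.2**

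| Output | Hematology | Biochemistry | Urinalysis |
|---|---|---|---|
| By-visit statistics and change from baseline | yes | yes | no |
| Graded summary and shift to worst post-baseline grade | yes | yes | no |
| Mean and mean-change plots | yes | yes | no |
| Subject listing | yes | yes | yes |

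**2. Does another section supply a urine summary?** SAP 8.5 names hematology and chemistry only. SAP 5.2.4 concerns collection. SAP 8.1 says how categorical variables are to be presented when they are summarised; it does not create a table.

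**3. Is a substitute stated?** For physical examination, SAP 8.5.5 says that clinically significant findings will be captured as adverse events, which explains why that endpoint has no table. No equivalent sentence exists for urinalysis, so the omission is not shown to be deliberate.

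**4. What reaches a table by another route?** Under protocol 8.6.1.1 a laboratory abnormality is recorded as an adverse event if it worsens from baseline with symptoms, changes study medication, needs intervention or a change in combination therapy, or is judged clinically significant. Protocol 8.4 adds abnormalities that change management, including extra monitoring. SAP 8.5.1 tabulates all TEAEs. Creatinine and urea or BUN are summarised as biochemistry. What remains outside every table is a urine change that meets none of these criteria.

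**5. How much data is involved?** Protocol 4.3.3 and Appendix 1 put a urine test on Day 1 of each cycle from Cycle 2, and two-cycle dispensing starts only at Cycle 7 (Appendix 1, note 14). Cycles 2 to 7 give 6 post-baseline Day 1 visits. With 30 patients, 6 × 30 = 180 scheduled panels. This is a ceiling for those visits, because it assumes that every patient stays on treatment to Cycle 7 Day 1. It measures the data left unsummarised, not the abnormalities missed.

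**The case against.** The strongest reply is that little would be lost. The adverse-event route is broad, and it has worked in this programme: in the Chinese phase I study (protocol 1.5), positive urine leukocytes in one subject was reported as a grade 1 TEAE. With 30 patients and no hypothesis testing, a listing can be read by eye. Protocol 10.1 leaves detailed methods to the SAP, and 10.6.3 requires a cross-tabulation only for severity 3 or higher.

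Much of this stands. It limits the gap to changes not recorded as adverse events, and it makes the gap one of summarising. It does not close the gap. The endpoint in 7.2 is change from baseline, not events selected by investigators, and 10.6.3 also promises descriptive statistics of abnormalities.

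Three stronger readings are tempting and are not supported:

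- A reader might infer that the study report would hold no count of proteinuria or hematuria, or would not report urinalysis at all. Abnormalities recorded as adverse events are counted, and every value is listed.
- A reader might infer an established renal toxicity in patients. The findings in protocol 1.3 come from rat and dog studies. They describe tubular changes and droplets inside epithelial cells and do not report proteinuria. The link to urine protein is an inference.
- A reader might size the gap from the acute kidney injury or renal TEAE rates in protocol Table 1. Those are adverse events, which SAP 8.5.1 already tabulates, so they do not measure what is missing.

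**Conclusion.** The point holds in a limited form. The SAP retains urinalysis as a safety endpoint and then plans no summary of it, so the change from baseline named in protocol 7.2 is not delivered for this panel and no reason is given. The consequence is confined to changes in urine protein, red cells, occult blood or other urine parameters that are not recorded as adverse events: these would be visible patient by patient but not counted.

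How many patients that concerns cannot be estimated, because the documents give no rate of urine changes that fall short of an adverse event. The conclusion rests on reading SAP 8.5 and 8.5.2 as the complete list of laboratory outputs. It affects no efficacy result. It is a small mismatch between the two documents that is worth correcting because the correction is cheap.

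**What to change.** In SAP 8.5, add urinalysis to the laboratory evaluations. In SAP 8.5.2, add a shift table from baseline to worst post-baseline category, with the number and percentage of patients with a new or worsened abnormality. Cover at least urine protein and red cells/occult blood, and use the treatment-period window that the SAP already applies to its other shift tables. Use normal/abnormal, or the categories collected in the eCRF, since protocol Table 5 gives no reporting scale. A split by concurrent creatinine grade is optional and goes beyond the protocol endpoint.

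If the sponsor prefers to keep a listing only, the SAP should say so and give the reason, as 8.5.5 does for physical examination.

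The cost is SAP wording and one or two descriptive tables. No new test, visit or data item is needed.

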8.5.4. Vital Signs

Descriptive statistics for vital signs (weight, BMI, body temperature, respiratory rate, pulse rate, systolic and diastolic blood pressure) values and the change from the baseline will be presented for each scheduled assessment time point.

Subject listing for vital signs will be provided.

8.5.5. Physical Examination

Clinically significant physical examination findings will be captured as AEs.

8.6. Pharmacokinetic Analyses

PK analyses will be presented in a separate PK analysis plan.

8.7. Other Analyses

Subgroup Analyses

Subgroup analyses for the endpoint of ORR will be conducted for the following subgroups:

- Severe cGVHD at screening (Yes / No)
- Number of organs involved at baseline (<4 / ≥ 4)
- Number of prior lines of therapy (1 / ≥ 2)
- Duration of cGVHD before enrollment (by 50th percentile)
- Lung involvement at baseline (Yes / No)
- Prior Ruxolitinib (Yes / No)
- Prior ibrutinib (Yes / No)

9. References

NMPA : Statistical Principles for Clinical Trials. 2016

NMPA : Guidance for Data Management and Statistical Analysis Plan and Report in Clinical Trial. 2016
